#### 5.3 VITAL SIGNS

#### 5.3.1 Available data

The following vital signs parameters are collected: heart rate, systolic (SBP) and diastolic blood pressure (DBP) in supine position, body temperature, body weight.

#### 5.3.2 Derivation rules

	Heart rate (bpm)	SBP (mmHg)	DBP (mmHg)	Temperature (°C)
Low	<40	<90	<45	<35.8
Normal	40-100	90-150	45-90	35.8-37.5
High	>100	>150	>90	>37.5

Abnormalities are defined in below table.

Note: For the worst-case analysis visit, as defined in section 2.2.5, an additional category low + high is defined in case there are both low and high post-baseline values.

BMI will only be used in the C-GTI derivations.

#### 5.3.3 Presentation of results

Vital signs parameters (except BMI) will be summarized by means of descriptive statistics at each analysis visit. Actual values and changes from baseline will be shown in the same table.

Abnormalities will be presented as cross-tabulations of the abnormality at each postbaseline analysis visit and at the worst-case analysis visit versus the baseline abnormality. This table will also show numbers of participants with treatmentemergent abnormalities (see Definition of terms). The denominator for the percentage is the total number of participants per treatment and per analysis visit in the Safety analysis set.

SGS	Statistical Analysis Plan	
ARGX-113-1905	Final analysis	Final 1.0 of 26APR2024

Tables to be produced for the topline results (see list of outputs in section 8.1) will show data for PV+PF participants as well as for PV participants.

All vital signs data will be listed, but only for participants with any post-baseline abnormality or clinically significant value.

#### 5.4 ELECTROCARDIOGRAMS

#### 5.4.1 Available data

The following electrocardiogram (ECG) parameters will be collected: heart rate (HR), QRS interval, PR interval, RR interval, QT interval, QTcF and QTcB.

#### 5.4.2 Derivation rules

Abnormalities for HR, QRS and PR interval are defined in below table.

	HR (bpm)	PR (ms)	QRS (ms)
Low	<40	<120	-
Normal	40-100	120-220	0-120
High	>100	>220	>120

Note: For the worst-case analysis visit, as defined in section 2.2.5, an additional category low + high is defined in case there are both low and high post-baseline values.

For QTc interval (ms), the following categories are defined:

- Actual values:
  - $\circ \leq 450 \text{ (normal)}$
  - o ]450; 480]
  - o ]480; 500]
  - o > 500
- Changes:
  - $\circ \leq 30 \text{ (normal)}$
  - o ]30; 60]
  - o > 60

Document template OTH.STAT.010 v3

Note: The worst-case, as defined in section 2.2.5, is the highest value and associated change.

#### 5.4.3 Presentation of results

Uncorrected QT interval will only be listed, RR interval will not be displayed.

Continuous ECG parameters will be summarized by means of descriptive statistics at each analysis visit. Actual values and changes from baseline will be shown in the same table.

Abnormalities of the actual values will be presented as cross-tabulations of the abnormality at each post-baseline analysis visit, and at the worst-case analysis visit

SGS	Statistical Analysis Plan	
ARGX-113-1905	Final analysis	Final 1.0 of 26APR2024

versus the baseline abnormality. This table will also show numbers and cumulative numbers (QTcF and QTcB only) of participants with treatment-emergent abnormalities (see Definition of terms). The denominator for the percentage is the total number of participants per treatment and per analysis visit in the Safety analysis set.

Abnormalities of the QTcF and QTcB changes from baseline will be presented as a tabulation of the change from baseline abnormality at each post-baseline analysis visit and at the worst-case analysis visit. This table will also show cumulative numbers over decreasing change from baseline abnormalities of participants. The denominator for the percentage is the total number of participants per treatment and per analysis visit in the Safety analysis set.

Tables to be produced for the topline results (see list of outputs in section 8.1) will show data for PV+PF participants as well as for PV participants.

All ECG data will be listed, but only for participants with any post-baseline abnormality or clinically significant value or change.

#### 5.5 **Physical examination**

#### 5.5.1 Available data

Physical examination results per body system will be available.

#### 5.5.2 Presentation of results

Abnormal physical examination results will be listed.

Final analysis

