3. OBJECTIVES AND ENDPOINTS

Objectives	Endpoints				
Primary					
• To assess the safety of treatment, extended treatment, and retreatment with efgartigimod PH20 SC in participants with PV or PF	• Incidence and severity of treatment-emergent adverse events (TEAEs), adverse events of special interest (AESIs), and serious adverse events (SAEs) by system organ class (SOC) and preferred term (PT)				
	• Vital sign measurements, physical examinations, electrocardiograms (ECGs), and clinical laboratory safety evaluations				
Secondary					
• To evaluate the efficacy of efgartigimod PH20 SC treatment in PV and PF	Proportion of PV participants who achieve CRmin				
	• Proportion of PV and PF participants who achieve CRmin				
	• Time to DC				
	• Time to CR				
	• Time to CRmin				
	• Time to CRoff				
	• Time to flare				
	• Rate of treatment failure				
	• Rate of flare				
	• Cumulative prednisone dose over the trial				
	• Pemphigus Disease Area Index (PDAI) at each visit				
• To assess the health impact of glucocorticoid (GC) use in participants with PV or PF	• Composite Glucocorticoid Toxicity Index (C-GTI) comprising the Aggregate Improvement Score (AIS) and the Cumulative Worsening Score (CWS)				
• To evaluate the effects of efgartigimod PH20 SC on quality of life (QoL) in participants	• EuroQol 5-Dimension 5-Level (EQ-5D-5L) score				
with PV or PF	• Autoimmune Bullous Disease Quality of Life (ABQOL) score				
• To evaluate the pharmacokinetics (PK) of efgartigimod PH20 SC in participants with PV or PF	• Efgartigimod serum concentrations				
• To evaluate the PD of efgartigimod PH20 SC in participants with PV or PF	• Total IgG and subtype (IgG1, IgG2, IgG3, IgG4) serum levels				
	• Anti-Dsg-1 and -3 autoantibodies serum levels				

Objectives	Endpoints			
• To evaluate the immunogenicity of efgartigimod in participants with PV or PF	• Incidence and prevalence of antidrug antibodies (ADA) against efgartigimod (serum levels)			
• To explore feasibility of self-administration of efgartigimod PH20 SC	• Percentage of participants who performed self-administration			
	• Percentage of caregivers who administered the injection to the participant			
	• Number of visits needed for the participant or caregiver to be competent to start administering efgartigimod PH20 SC			
	• Frequency of self- or caregiver-supported administration at home			
Exploratory				

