9.1.2. Safety (Primary Endpoints)

All clinical safety outcomes will be reported using descriptive statistics in the form of summary tables. Wherever it is suitable, respective graphical displays will be presented along with the summary tables. The main safety primary endpoints will be summaries from the following sections of each endpoint.

- Incidence and severity of:
 - TEAEs
 - AESIs
 - SAEs
- Vital signs and physical examination
- ECG
- Clinical laboratory test results (hematology, clinical chemistry, urinalysis)

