9.5.4. Demographic and Baseline Characteristics, and Concomitant Medication

Participant demographic and baseline characteristic data, including prior and concomitant therapies will be summarized using standard summary statistics (Section 9.1) and listed.

9.5.5. **Primary Endpoint(s)**

Exposures to IMP and prednisone will be summarized. The safety analysis will be analyzed overall but also by status at entry into ARGX-113-1905.

Summaries of TEAEs and other safety parameters will be provided by treatment group. Summary statistics will be presented for all other safety endpoints including vital signs, physical examinations, laboratory values and ECGs.

AEs will be classified using the latest version of the MedDRA classification system. AEs and AESIs will be listed corresponding to SOC and MedDRA PT. Multiple occurrences of a single PT in a participant will be counted only once at the maximum severity/grade. Any AEs with missing severity or relationship to IMP will be classified as severe and treatment-related, respectively. All AEs will be summarized by relatedness to IMP. Any AEs leading to death or discontinuation of IMP will also be summarized. Clinically significant laboratory abnormalities will be summarized descriptively.

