#### 5.2.3 Presentation of results

The statistical analysis will present results in standardized units, except for eGFR, which will be reported in mL/min/ $1.73m^2$ .

Continuous laboratory parameters will be summarized by means of descriptive statistics of the actual values and changes from baseline at each analysis visit. For albumin and LDL-C, also percent changes from baseline will be shown. Categorical parameters will be listed only.

Laboratory abnormalities will be presented as cross-tabulations of the abnormality at each post-baseline analysis visit and at the worst-case analysis visit versus the baseline abnormality. This table will also show numbers of participants with treatment-emergent abnormalities (see Definition of terms). The denominator for the percentage is the total number of participants per treatment and per analysis visit in

SGS	Statistical Analysis Plan	
ARGX-113-1905	Final analysis	Final 1.0 of 26APR2024

the Safety analysis set. Abnormalities will not be tabulated for those parameters for which toxicity grades are defined.

Laboratory toxicity grades will be presented as cross-tabulations of the toxicity at each post-baseline analysis visit and at the worst-case analysis visit versus the baseline toxicity. This table will also show numbers and cumulative numbers over decreasing toxicity grading of participants with treatment-emergent toxicities. The denominator for the percentage is the total number of participants per treatment and per analysis visit in the Safety analysis set. Parameters having toxicity grades defined in both directions (hypo and hyper) will be shown by direction.

Tables to be produced for the topline results (see list of outputs in section 8.1) will show data for PV+PF participants as well as for PV participants.

All laboratory data will be listed, but only for participants with any post-baseline abnormality/toxicity or clinically significant value.

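### Physical examination and categorical urinalysis belong to the primary safety endpoint and the protocol promises summaries of them, but the SAP only lists them and does not declare the change

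*SAP*

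**What the plan says.** Protocol section 3 sets out the non-AE part of the primary endpoint as "Vital sign measurements, physical examinations, electrocardiograms (ECGs), and clinical laboratory safety evaluations". Section 9.1.2 gives the reporting rule, "All clinical safety outcomes will be reported using descriptive statistics in the form of summary tables", and its list of main safety endpoints includes "Vital signs and physical examination" and a laboratory item that names urinalysis beside hematology and chemistry. Section 9.5.5 repeats the commitment, "Summary statistics will be presented for all other safety endpoints including vital signs, physical examinations, laboratory values and ECGs", and adds "Clinically significant laboratory abnormalities will be summarized descriptively".

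SAP 5.5.2 consists of one sentence on physical examination: "Abnormal physical examination results will be listed". SAP 5.2.3 gives continuous laboratory parameters descriptive statistics by visit and cross-tabulates abnormalities and toxicity grades against baseline. For the rest it says "Categorical parameters will be listed only".

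Protocol 9.1.1 allows minor changes of method without an amendment, provided they are documented in the SAP and the trial report. SAP 6.1 records three matters: visit labels, the normalized cumulative prednisone dose by period, and the proportion reaching complete remission off therapy. It records nothing about safety presentation.

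**The concern.** The mismatch sits in the primary endpoint. Vital signs and ECG, which belong to the same endpoint, each get descriptive and cross-tabulated output. Physical examination and category-type urinalysis do not, and nothing in the SAP shows that this was a decision.

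A listing restricted to abnormal results, or to participants with an abnormal value, carries no denominator and no shift from baseline. A reader of the report could not say from it how many participants were normal at roll-over and abnormal later in a given body system, or how many changed from a negative to a positive dipstick result. Both assessments are collected repeatedly: Table 1 of the protocol schedules them at roll-over, at 12 four-weekly visits to week 48, and at the end-of-treatment visit. That is 1 + 12 + 1 = 14 open-label visits, before follow-up.

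**Working it through.** The plan gives no figure to reproduce here. The check compares what the protocol promises with what the SAP delivers.

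| Component | Protocol promise | SAP text | Table in SAP 8.1 | Listing in SAP 8.2 |
|---|---|---|---|---|
| Vital signs | Summary (9.1.2, 9.5.5) | Descriptive and cross-tabulated (5.3.3) | 14.3.3.1, 14.3.3.2 | 16.2.9.1 |
| ECG | Summary (9.1.2, 9.5.5) | Descriptive and cross-tabulated (5.4.3) | 14.3.4.1 to 14.3.4.4 | 16.2.10.1 |
| Laboratory, continuous | Summary (9.1.2, 9.5.5) | Descriptive; abnormality or grade cross-tabulated (5.2.3) | 14.3.2.1 to 14.3.2.5 | 16.2.8.1 |
| Laboratory, categorical | Summary (9.1.2, 9.5.5) | Listed only (5.2.3) | None | 16.2.8.1 |
| Clinically significant laboratory values | Descriptive summary (9.5.5) | Used only to select participants for the listing (5.2.3) | None | 16.2.8.1 |
| Physical examination | Summary (9.1.2, 9.5.5) | Abnormal results listed (5.5.2) | None | 16.2.11.1 |

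**How much of urinalysis is affected.** The SAP does not state the data type of any urinalysis parameter, so this step is an assumption. Ten dipstick parameters are named. Specific gravity and pH are taken as numeric, which leaves 10 − 2 = 8. Of those, seven are taken as categorical: protein, glucose, ketones, blood, bilirubin, nitrite and leukocyte esterase. Urobilinogen is left open. At the extremes, if the laboratory reports every parameter as a category, all 10 are listed only; if it reports every one as a number, none is. Color, clarity and microscopy come on top.

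**Whether the abnormality cross-tabulation rescues the categorical results.** SAP 5.2.2 defines low, normal and high against numeric range limits for parameters without a toxicity grade. Specific gravity and pH fit that rule and would appear in tables 14.3.2.1 and 14.3.2.4. No rule is given for classifying a category result, and 5.2.3 says such parameters are not tabulated.

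**Whether adverse events carry the same information.** Protocol 8.3.1 and 8.3.6 turn clinically significant examination and laboratory findings into adverse events, and SAP 5.1.3 tabulates those with counts, percentages and rates. The route has two filters. Section 8.3.6 lets an abnormal laboratory value go unreported as an adverse event when it fits a current diagnosis. Section 10.3.1 excludes findings tied to the underlying disease unless they are more severe than expected. Adverse event tables also show no shift from baseline.

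**Whether the change is declared.** It is not; the three entries in SAP 6.1 concern other matters.

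**The case against.** The strongest defence is that nothing clinically important goes uncounted. Findings that matter become adverse events and are tabulated by system organ class and preferred term. All infections are events of special interest, with tables overall, by disease status and by relatedness (14.3.1.12.1, 14.3.1.12.2 and 14.3.1.13), so a urinary tract infection would appear as a preferred term. Glucose control is followed through HbA1c. It has no grade in SAP 9.2 and therefore gets the low/normal/high cross-tabulation, and it also feeds the composite glucocorticoid toxicity scores in table 14.2.1.8.1. On this view a one-line entry in SAP 6.1 would settle the matter.

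Most of that stands, and it rules out two stronger readings:

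- A reader might infer that physical examination and urinalysis have no analysis at all. The documents do not support this: abnormal results are listed, most significant findings enter the adverse event tables, and numeric urinalysis parameters are summarised.
- A reader might infer that urinary infection or steroid-related hyperglycaemia would go uncounted. That does not follow either, given the special-interest tables and HbA1c. The 3 of 34 participants (8.8%) with urinary tract infection in the phase 2 pemphigus study, shown in protocol 8.4.8, came from adverse event reporting. This SAP keeps that reporting, so the figure does not measure any loss.

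The defence does not remove the conflict. The protocol promised summaries of these components themselves, the adverse event route is filtered, and the departure is undeclared although protocol 9.1.1 requires it to be documented.

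**Conclusion.** The point holds as an undeclared mismatch between protocol and SAP on components of the primary safety endpoint. Physical examination and categorical laboratory results are listed but not summarised, and clinically significant laboratory values have no summary of their own.

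The consequence is minor. What is lost is participant counts and shifts from baseline for these components: mainly raw dipstick positivity, examination abnormalities judged not clinically significant, and the laboratory findings exempted from adverse event reporting. The study is descriptive, with no hypothesis (protocol 9.2) and no sample size calculation (9.3), so no error rate or estimate depends on it. SAP 1.3 puts the ceiling at about 213 participants. The Safety set can only be that or smaller, because it excludes anyone not dosed in this study.

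The physical examination part rests on no assumption. The urinalysis part rests on the seven named dipstick parameters being reported as categories, which the laboratory can confirm.

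**What to change.** - In SAP 5.5.2 and 8.1, add the number and percentage of Safety-set participants with a new post-baseline physical examination abnormality, by body system. SAP 5.5.1 says results per body system are available.
- In SAP 5.2.3 and 8.1, add a shift table of baseline against worst post-baseline result for the categorical dipstick parameters. State which parameters are categorical and which categories count as abnormal, so that the worst-case visit in SAP 2.2.5 can be applied.
- In the same sections, add a count of participants with clinically significant laboratory values. The SAP already uses that attribute to select participants for the laboratory listing.
- Present all three by treatment and total, over the treatment and follow-up phases, as for the other safety tables.
- Record in SAP 6.1 any component that is deliberately left as a listing, with the reason.

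The cost is SAP wording and up to three extra tables from data already collected. The drawback is partial overlap with the adverse event tables, most of all for the clinically significant laboratory count. No protocol change is needed.

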## 6. CHANGES TO THE PLANNED ANALYSIS

# 6.1 CHANGES NOT COVERED BY PROTOCOL AMENDMENTS BEFORE DATABASE LOCK

Analysis visit labels deviate from the visit labels in the schedule of assessments of the protocol to accommodate the example in the ICH E3 guideline annex III.

The following extra endpoints will be derived, which are not covered in the CTP (see section 4.1.2.1 and 3.4.2):

- NCPD defined for different periods
- Proportion of participants achieving CRoff

# 6.2 CHANGES NOT COVERED BY PROTOCOL AMENDMENTS AFTER DATABASE LOCK

Not applicable.

#### 6.3 CHANGES TO THE FINAL STATISTICAL ANALYSIS PLAN

Not applicable.

7.

Final analysis

## 8. LIST OF TABLES, LISTINGS AND FIGURES

#### 8.1 TABLES

Note: tables to be produced for the topline results (TL) are indicated in last column

#### GENERAL CHARACTERISTICS

14.1.1.1	Analysis Sets and Disease Status at Roll-over	ROLL	TL
14.1.1.2	Participant Disposition by Country and Site	ROLL	
14.1.1.3	Participant Disposition by Analysis Visits	ROLL	
14.1.1.4	Analysis Phase/Period Duration	ROLL	
14.1.1.5.1	Treatment Discontinuation	SAF	TL
14.1.1.5.2	Treatment Discontinuation by Disease Status at Roll-over	SAF	TL
14.1.1.6	Study Discontinuation	ROLL	
14.1.1.7	Major Protocol Deviations	ROLL	
14.1.1.8	Minor Protocol Deviations	ROLL	
14.1.2.1.1	Demographic Data	ROLL	TL
14.1.2.1.2	Demographic Data by Disease Status at Roll-over	ROLL	TL
14.1.2.2.1	Baseline Disease Characteristics	ROLL	TL
14.1.2.2.2	Baseline Disease Characteristics by Disease Status at Roll-over	ROLL	TL
14.1.2.3	Concomitant Therapies by ATC Class (Level 1 and 3) and Generic Term	SAF	
14.1.2.4.	Concomitant Prednisone Administration by ATC Class (Level 1 and 3) and Generic Term	SAF	TL
14.1.2.5.1	IMP Administration	SAF	TL
14.1.2.5.2	IMP Administration by Disease Status at Roll-over	SAF	TL
14.1.2.6	IMP (Self-)Administration Training of Participants	SAF	
14.1.2.7	IMP (Self-)Administration Training of Caregivers	SAF	
14.1.2.8	IMP Self-Administration	SAF	
EFFICACY			
14.2.1.1.1	Proportion of Participants Who Achieved CRmin	ROLL	TL
14.2.1.1.2	Proportion of Participants Who Achieved CRmin by Disease Status at Roll-over	ROLL	TL
14.2.1.1.3	Proportion of Participants Who Achieved CRoff	ROLL	TL
14.2.1.1.4	Proportion of Participants Who Achieved CRoff by Disease Status at Roll-over	ROLL	TL
14.2.1.2.1	Time to CRmin: Descriptive Statistics	ROLL	TL
14.2.1.2.2	Time to CRmin: Descriptive Statistics by Disease Status at Roll- over	ROLL	TL
14.2.1.2.3	Time to CRoff: Descriptive Statistics	ROLL	TL
14.2.1.2.4	Time to CRoff: Descriptive Statistics by Disease Status at Roll-over	ROLL	TL
14.2.1.2.5	Time to DC: Descriptive Statistics	ROLL	TL
Document templ	Page 60 of 84		IFTARY

SGS	Statistical Analysis Plan	
ARGX-113-1905	Final analysis	Final 1.0 of 26APR2024

14.2.1.2.6	Time to DC: Descriptive Statistics by Disease Status at Roll-over	ROLL	TL
14.2.1.2.7	Time to CR: Descriptive Statistics	ROLL	TL
14.2.1.2.8	Time to CR: Descriptive Statistics by Disease Status at Roll-over	ROLL	TL
14.2.1.3.1	NCPD: Descriptive Statistics	ROLL	TL
14.2.1.3.2	4.2.1.3.2 NCPD: Descriptive Statistics by Disease Status at Roll-over		TL
14.2.1.3.3	Cumulative Prednisone Dose: Descriptive Statistics	ROLL	TL
14.2.1.3.4	Cumulative Prednisone Dose: Descriptive Statistics by Disease Status at Roll-over	ROLL	TL
14.2.1.4.1	Proportion of Participants Who Experienced Flare After CRmin	ROLL	TL
14.2.1.4.2	Proportion of Participants Who Experienced Flare After CRmin by Disease Status at Roll-over	ROLL	TL
14.2.1.4.3	Time to Flare After CRmin: Descriptive Statistics	ROLL	TL
14.2.1.4.4	Time to Flare After CRmin: Descriptive Statistics by Disease Status at Roll-over	ROLL	TL
14.2.1.5.1	Number of Flares – Descriptive Statistics	ROLL	TL
14.2.1.5.2	Number of Flares – Descriptive Statistics by Disease Status at Roll- over	ROLL	TL
14.2.1.6.1	Proportion of Treatment Failures	ROLL	TL
14.2.1.6.2	Proportion of Treatment Failures by Disease Status at Roll-over	ROLL	TL
14.2.1.7.1	PDAI in PV Participants: Descriptive Statistics of Actual Values, Changes from Baseline, Changes from 1904 Baseline and Changes from Treatment Period Baseline by Visit	ROLL	
14.2.1.7.2	PDAI in PV Participants: Descriptive Statistics of Actual Values, Percent Changes from Baseline, Percent Changes from 1904 Baseline and Percent Changes from Treatment Period Baseline by Visit	ROLL	
14.2.1.7.3	PDAI in PV+PF Participants: Descriptive Statistics of Actual Values, Changes from Baseline, Changes from 1904 Baseline and Changes from Treatment Period Baseline by Visit	ROLL	TL
14.2.1.7.4	PDAI in PV+PF Participants: Descriptive Statistics of Actual Values, Percent Changes from Baseline, Percent Changes from 1904 Baseline and Percent Changes from Treatment Period Baseline by Visit	ROLL	
14.2.1.8.1	C-GTI: Descriptive Statistics of CWS and AIS at Week 26, Week 52 and Overall	ROLL	
14.2.1.9.1	ABQOL: Frequency Tabulation of 17 Items by Visit	ROLL	
14.2.1.9.2	ABQOL: Descriptive Statistics of Actual Values and Changes from Baseline in ABQOL Total Score by Visit	ROLL	
14.2.1.10.1	EQ-5D-5L: Frequency Tabulation of 5 Dimensions by Visit	ROLL	
14.2.1.10.2	EQ-5D-5L: Descriptive Statistics of Actual Values and Changes from Baseline in VAS Score by Visit	ROLL	
PHARMAC	OKINETICS		
14.2.2.1	Descriptive Statistics of Efgartigimod Serum Concentration over time	SAF	
D	Page 61 of 84		

•	SGS	Statistical Analysis Plan	
	ARGX-113-1905	Final analysis	Final 1.0 of 26APR2024

